- E. Recruitment Procedure: Patients undergoing an ACL reconstruction with autologous BPTB graft harvest will be asked prior to surgery for their participation in this study after considering the inclusion/exclusion criteria. Informed consent will be obtained any time after the patient is booked for surgery (usually 2-3 weeks before surgery) and before the day of surgery (not on the day of surgery). Patients will be blinded to treatment randomization.

F. Data Collection: Data collection will be prospective

- Pre-operative data collection requiring patients to fill out a form will include: the IKDC Demographic Form (see below) which will require approximately 5 minutes of time during a preoperative office visit.

IKDC Demographic Form

IKDC DEMOGRAPHIC FORM

Your Full Name _____

Your Date of Birth _____ / _____ / _____
Day Month Year

Your Social Security Number ____ - ____ - ____ **Your Gender:** **Male** **Female**

Occupation _____

Today's Date _____ / _____ / _____
Day Month Year

The following is a list of common health problems. Please indicate "Yes" or "No" in the first column, and then skip to the next item. If you do have the problem, please indicate in the second column if you receive medications or some other type of treatment for the problem. In the last column, indicate if the problem limits any of your activities.

	Do you have the problem?		Do you receive treatment for it?		Does it limit your activities?	
	Yes	No	Yes	No	Yes	No
Heart disease						
High blood pressure						
Asthma or pulmonary disease						
Diabetes						
Ulcer or stomach disease						
Bowel disease						

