- Some college
- Graduated from college
- Postgraduate school or degree

6. Activity level

- Are you a high competitive sports person?
- Are you well-trained and frequently sporting?
- Sporting sometimes
- Non-sporting

- Pre-operative objective data collection will include:
 - Time from injury to surgery, and a radiographic grading of osteoarthritis using the Kellgren-Lawrence classification scale performed by one senior musculoskeletal radiologist (DK).
- Intra-operative data collection will include: Outerbridge classification of medial, lateral, patellofemoral compartments osteoarthritis, blood loss, time of surgery, tourniquet time, meniscal pathology and its treatment. A sample of intraoperative data sheets is listed below:

2000 IKDC SURGICAL DOCUMENTATION FORM

Patient's Name: _____ Date of Index Procedure: ____/____/____
Day Month Year

[figure not shown]
Postoperative Diagnosis:

1. _____
2. _____
3. _____

Status After Procedure:

ARTICULAR CARTILAGE STATUS:

Document the size and location of articular cartilage defects on these figures according to the ICRS mapping system⁵.

[figure not shown]
MENISCUS STATUS:

- Procedure: medial meniscectomy lateral meniscectomy
 medial meniscal repair lateral meniscus repair
 medial meniscal transplant lateral meniscal transplant
 medial abrade & trephine lateral abrade & trephine

Right Knee

Left Knee

Document tears of the menisci or meniscectomy on these figures

Medial:

- Normal 1/3 Removed 2/3 Removed 3/3 Removed
 Circumferential Hoop Fibers: Intact Disrupted
 Remaining Meniscal Tissue: Normal Degenerative changes
 Stable tear Unstable tear
 Tear left in situ

Lateral:

- Normal 1/3 Removed 2/3 Removed 3/3 Removed
 Circumferential Hoop Fibers: Intact Disrupted
 Remaining Meniscal Tissue: Normal Degenerative changes
 Stable tear Unstable tear
 Tear left in situ

LIGAMENT STATUS:

Procedure:

- | | | |
|--|--|--|
|  ACL repair |  Intraarticular ACL reconstruction |  Extraarticular ACL reconstruction |
|  PCL repair |  Intraarticular PCL reconstruction |  Posterolateral corner repair/reconstruction |
|  Medial collateral ligament repair/reconstruction | | |
|  Lateral collateral ligament repair/reconstruction | | |

[figure not shown]
Graft:

- | | | |
|--|--|--|

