|  Autologous patella tendon |  Hamstring tendons |  Quadriceps tendon |
|  Other _____ | | |

Previous Graft Harvest:

- | | | |
|--|--|--|
|  Autologous patella tendon |  Hamstring tendons |  Quadriceps tendon |
|--|--|--|

Document drill hole placement for ligament reconstruction on these figures.

- Post-operative data collection will include both subjective and objective outcomes measures.
 - Subjective outcomes of donor site morbidity will include VAS for ADL's, VAS for kneeling, IKDC subjective knee evaluation form, and a return to sports/subjective performance questionnaire. Each post operative office visit will require approximately 10 minutes of patient time to fill out the subjective questionnaires.
 - Collected at 14days and 1,3,6,12,18 and 24 months

Example of how a VAS questionnaire is converted to numerical data points:

[figure not shown]

Figure 1. A, a VAS for recording the severity of pain. The question posed would read, “How bad is the pain at its worst?” B, the patient places a mark at what he feels is the appropriate point on the line. C, through simple measurement techniques, this graphic representation may be converted to a numerical value.

Visual Analog Scale

Activities of Daily Living

For each question, place a mark on the line between the two descriptions which you think describes your knee relative to the two extremes.

No Knee Discomfort
With Activities of Daily

Constant Knee Pain
With Activities of Daily

Visual Analog Scale

Kneeling Pain

For each question, place a mark on the line between the two descriptions which you think describes your knee relative to the two extremes.

No Knee Discomfort
With Kneeling

Unable to Kneel
Due to Knee Pain

IKDC Subjective Knee Evaluation Form

2000 IKDC SUBJECTIVE KNEE EVALUATION FORM

Your Full Name _____

Today's Date: ____/____/____
Day Month Year

Date of Injury: ____/____/____
Day Month Year

SYMPTOMS*:

*Grade symptoms at the highest activity level at which you think you could function without significant symptoms, even if you are not actually performing activities at this level.

1. What is the highest level of activity that you can perform without significant knee pain?

- 4 Very strenuous activities like jumping or pivoting as in basketball or soccer

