ΔCrepitus Ant. Compartment	none	moderate	mild pain	>mild pain				
ΔCrepitus Med. Compartment	none	moderate	mild pain	>mild pain				
ΔCrepitus Lat. Compartment	none	moderate	mild pain	>mild pain				
5. Harvest Site Pathology	none	mild	moderate	severe				
6. X-ray Findings								
Med. Joint Space	none	mild	moderate	severe				
Lat. Joint Space	none	mild	moderate	severe				
Patellofemoral	none	mild	moderate	severe				
Ant. Joint Space (sagittal)	none	mild	moderate	severe				
Post. Joint Space (sagittal)	none	mild	moderate	severe				
7. Functional Test								
One Leg Hop (% of opposite side)	≥90%	89 to 76%	75 to 50%	<50%				
**Final Evaluation								

G. Experimental Design

Patients will be randomized using a computer generated randomization table (simple randomization) into one of two treatment arms:

(1) Autologous BPTB ACL reconstruction followed by application of PRP soaked bone chips = Treatment

(2) Autologous BPTB ACL reconstruction = Control

The patient, research personnel and individuals collecting all objective outcome measures will be blinded to the randomization. The operating surgeons (SJM or BB) will evaluate the subjects pre and post operatively but will not contribute any of their objective data collection to the study. Randomization and patient assignments will be done through sequentially numbered opaque sealed envelopes by the circulating nurse in the OR at the time of surgery. The randomization will not be stratified according to surgeon but rather-according to treatment arm. Randomization information will then be recorded and placed into a sealed envelope with the patients' randomization ID and deposited into a locked reception box. This box will only be opened upon completion of the study.

H. Research Procedure

ACL reconstruction

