APPENDIX B

Data Collection Sheet- Subjective

Pt. ID #	VAS ADL	VAS Kneeling	RSQ	IKDC
001				
002				
003				
004				
005				

Return to Sports Questionnaire

- 6months post op

Visual Analog score for ADL

- 14d, 1, 3, 6, 12, 18, 24 months follow up

Visual Analog score for Kneeling:

- 14d, 1,3,6,12,18, 24 months follow up

IKDC subjective knee evaluation form

- 14d, 1,3,6,12,18, 24 months follow up

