APPENDIX C

Data Collection Sheet- Objective

Pt. ID #	XR tunnel placement	XR Donor Site Healing	MRI Donor Site Healing	IKDC	Quadriceps Strength	ROM
001						
002						
003						
004						
005						

Radiographic healing

- 3 months – XR assessment of tunnel placement and donor site healing
- 6 months - MRI Assessment of Donor Site Healing

IKDC Knee examination form

- 14d, 1,3,6,12,18 and 24 months follow up

ROM Measurements

- 14d, 1,3,6,12,18 and 24 months follow up

Quadriceps Strength

- Dynamometry scale

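### Pain and knee function are first scored 14 days after surgery; adding the three patient-completed forms to the existing pre-operative visit would be a cheap improvement, with an uncertain gain in precision.

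*Combined protocol and SAP*

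**What the plan says.** **Before surgery.** Section F of the combined protocol and SAP lists one patient-completed form: "Pre-operative data collection requiring patients to fill out a form will include: the IKDC Demographic Form". It covers comorbidities, smoking, height, weight, race, education and activity level. The objective items are "Time from injury to surgery, and a radiographic grading of osteoarthritis using the Kellgren-Lawrence classification scale performed by one senior musculoskeletal radiologist". None of these is a pain or knee-function score. Section G says that the surgeons see patients before the operation, but that their assessments do not enter the study data.

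**After surgery.** The VAS for daily activities, the VAS for kneeling and the IKDC subjective form fall under the line "Post-operative data collection will include both subjective and objective outcomes measures", with the schedule "Collected at 14days and 1,3,6,12,18 and 24 months". Appendix B agrees, giving "14d, 1, 3, 6, 12, 18, 24 months follow up" for the daily-activities VAS and the same time points for the other two. In Appendix C the IKDC examination and range of motion follow "14d, 1,3,6,12,18 and 24 months follow up".

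**Analysis and allocation.** Section I plans a mixed model with Group and Time, where every level of Time is post-operative and no covariate is named. It also promises summaries of baseline data without saying what these include. Section G allocates by a "computer generated randomization table (simple randomization"), not stratified by surgeon.

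**The concern.** The pre-operative score is the usual covariate for a pain or function scale. Here it is not collected, although patients already sit down with a form before surgery. With simple randomisation of about 100 patients, the arms can differ by chance in how painful or limited the knees were before the operation, and nothing in the planned data would show it.

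Three things are lost:

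- the precision that adjustment could add;
- the ability to describe pre-operative pain and function by arm;
- the ability to compare pre-operative status between completers and patients lost to follow-up, where section I allows for up to 30% loss at two years.

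The IKDC subjective form has one look-back item, but it asks about function before the injury, not before the operation, and it is first asked at 14 days. The scores cannot be recovered once surgery has taken place.

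**Working it through.** **Inputs from section I:** difference 2 points, SD 3.0, alpha 0.05, 35 evaluable patients per arm, 80% power, 30% loss, 50 enrolled per arm. Sidedness is not stated; two-sided is assumed, because a one-sided test would need only 28 per arm and does not match. **Assumed, not in the documents:** the correlation r between pre-operative and post-operative scores, taken from 0 to 0.5.

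**1. The plan's own figure.** Normal formula: n = 2 × [3.0 × (1.960 + 0.842) / 2]² = 35.3 per arm. Power at exactly 35 is 79.6%. Inflation: 35 / (1 − 0.30) = 50. The plan's 35 and 50 reproduce to within rounding. With the t distribution (68 degrees of freedom), power at 35 per arm is 78.5%. This is the unadjusted reference below.

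**2. Power with a baseline covariate.** Residual SD = 3.0 × √(1 − r²). Estimating the slope costs one degree of freedom (67 remain) and multiplies the expected variance of the treatment difference by about 1 + 1/(N − 4). With N = 70 this is 1 + 1/66 = 1.015. The noncentrality is 2 / [residual SD × √(2/35 × 1.015)].

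| r | Variance removed (r²) | Residual SD | Power at 35 per arm |
|---|---|---|---|
| No covariate | – | 3.00 | 78.5% |
| 0 | 0% | 3.00 | 77.9% |
| 0.1 | 1% | 2.98 | 78.3% |
| 0.2 | 4% | 2.94 | 79.5% |
| 0.3 | 9% | 2.86 | 81.6% |
| 0.5 | 25% | 2.60 | 88.3% |

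The worst case is a loss of 78.5 − 77.9 = 0.6 points. Adjustment breaks even where r² is close to 1/66, that is, r of about 0.12. At r = 0.2 the gain is 1.0 point, at r = 0.3 it is 3.1 points, and at r = 0.5 it is 9.8 points. These figures describe one comparison at one time point, as the plan's own calculation does; they are not the power of the seven-visit mixed model.

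**3. Chance imbalance.** In SD units, the standard error of a difference in baseline means is √(2/n): 0.200 at 50 per arm and 0.239 at 35 per arm. A difference above 0.25 SD in either direction on a given score then has probability of about 21% (z = 0.25/0.200 = 1.25) and 30% (z = 0.25/0.239 = 1.05). Such differences are not rare, and on pain and function they would go unseen.

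**4. Feasibility.** Section F puts the whole set of post-operative questionnaires, including return to sports, at about 10 minutes, so 10 minutes is an upper limit for three of them. Consent precedes the day of surgery (section E), and the allocation envelope is opened in the operating room (section G). The scores would therefore be taken before randomisation, and blinding is unaffected.

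**The case against.** The strongest objection is that the benefit is weakest for the outcome on which the trial is sized. Section I is built on kneeling pain, which the protocol treats as morbidity of the graft donor site. That site does not exist before surgery, and section C excludes patients with earlier anterior knee pain or any previous knee injury. A pre-operative kneeling score would mostly reflect the ligament injury, over a restricted range, so a low correlation is plausible. This stands: for kneeling pain the gain may be near the low end of the table, and it could be slightly negative. It has less force for the daily-activities VAS and the IKDC form, which ask about knee pain, swelling, giving way and function more generally.

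A second objection is that the trial does not need the precision. The SD of 3.0 is deliberately conservative: section I gives an average of 2.0 across its three cited studies, and at SD 2.0 power with 35 per arm is about 98%. The 35 also assumes the full 30% loss. This too stands, and it means that the point is not a repair of an underpowered design.

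A reader might infer more than the documents support:

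- **That the trial is biased without a baseline.** It is not. Randomisation keeps the unadjusted comparison unbiased, and chance imbalance is already reflected in its standard error.
- **That balance cannot be checked at all.** Age, sex, BMI, activity level, time from injury, Kellgren-Lawrence grade, Outerbridge grade and meniscal findings are all recorded. Only balance on pre-operative pain and function is out of sight.
- **That any modest correlation would bring power to 80%.** At r = 0.2 it reaches 79.5% once the slope is paid for.
- **That every outcome needs a baseline covariate.** Imaging of donor-site healing and return to sports have no matching pre-operative value.

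**Conclusion.** The point holds as a low-cost improvement, not as an error in the plan. No pre-operative VAS or IKDC subjective score is scheduled, and the model has no baseline covariate, so chance imbalance in pre-operative pain and function cannot be seen or adjusted for. Nor can patients lost to follow-up be described on those scores.

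The effect on power ranges from a loss of 0.6 points to a gain of 9.8 points for r between 0 and 0.5, and exceeds about 3 points only if r is 0.3 or more. This rests on the plan's difference of 2 and SD of 3.0, a two-sided t comparison at one time point with 35 per arm, and an assumed correlation. A useful gain is more plausible for the daily-activities VAS and the IKDC form than for kneeling pain. The descriptive benefit does not depend on the correlation.

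**What to change.** In section F and Appendix B, add the VAS for daily activities, the VAS for kneeling and the IKDC subjective form to the existing pre-operative visit, completed after consent and before the day of surgery. In section I, prespecify the matching pre-operative score as a covariate in the mixed model for each of these three outcomes, keeping Time as the seven post-operative visits. List the three scores among the baseline data to be summarised by arm, and separately for completers and patients lost to follow-up. Do not extend the covariate to X-ray, MRI or return to sports.

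The cost is at most about 10 minutes of patient time at a visit that already takes place, one degree of freedom per model, and about 0.6 points of power if the correlation is zero. No extra staff or procedure is needed. The change helps only patients who have not yet had surgery.

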Will be performed using standard approved surgical technique. The surgeries will be performed by one of two senior surgeons (SJM or BB) and diagnostic arthroscopy will verify the inclusion criteria are met (no additional ligamentous injury, no osteochondral defect, and Outerbridge classification grade 2 or lower). After fixation of the graft and just prior to closure, the senior attending (SJM or BB) and any other research personnel present will leave the room so that application of either PRP soaked cancellous bone chips or non-treated cancellous bone chips to the graft harvest site can be performed in a manner that will maintain blinding. A surgical fellow or resident who will not be present for any portion of the outcomes data collection will do this and therefore, will not compromise the blinding of the study. The Patellar tendon will be closed over the material thus sealing it within the donor site and the wound will be closed using normal guidelines.

PRP Preparation

The PRP will be prepared directly in the operating room prior to the surgical intervention but after the patient has been placed under general anesthesia. The Arthrex ACP Double Syringe system will be used according to their manufacturing guidelines. The blood sample will be obtained by the anesthesiologist at the start of the case, just after the patients have been placed under general anesthesia via the same IV access utilized to administer the anesthesia. The Anesthesiologist will have no role in the data collection or surgical intervention aspect of the study. As the blood will be drawn after patients are asleep, they will remain blinded to their treatment arm and only those in the treatment arm will have blood withdrawn and no additional IV access will be necessary.

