For each patient in the treatment arm of the study, the anesthesiologist will withdraw 10cc of venous blood prior to the surgeon or research assistants having entered the room. The blood sample will be given to an OR assistant to prepare prior to the start of the case. The 10cc of venous blood will be mixed together with 1 cc of ACD-A (citrate anticoagulant) and centrifuged for 5 min at 1500 rpm. The blood sample will separate into red blood cells and a supernatant “buffy coat” layer containing platelets (PRP) and white blood cells. This Leukocyte rich prp layer will be approximately 3-5cc in volume and will be aspirated into the inner smaller diameter syringe of the double syringe system. Lastly, the PRP phase will be mixed together with .25cc of CaCl₂ and placed within a sterile specimen cup that is covered in aluminum foil so that no one can see what is inside. Once the graft has been harvested, the autologous cancellous bone chips retrieved will be added to the specimen cup by the scrub technician. The PRP and cancellous bone chips will be mixed together in a separate sterile preparatory area of the operating room. They will be left to soak within the concealed container until the end of the case when the chips and PRP will be placed together within the patellar bony defect. A separate member of the staff who is not involved in any of the postoperative data collection measures will do this. Prior to placement of the PRP soaked cancellous chips within the wound and closure, the primary surgeon (SJN or BB) and any personnel present who will also be present during the post operative time frame for outcomes measurements will leave the room.

Concealing the contents of the specimen cup, preparing the PRP and adding it to the specimen cups prior to the presence of any active participant in the study (Senior surgeon or otherwise) entering the room, and adding the prp soaked bone chips to the patellar defect without any active study members in the room ensures blinding.

I. Statistical Analysis/Data Management

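### Section H describes the foil-covered cup for PRP cases only; unless controls get the same cup, its presence in the operating room can signal the arm

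*Combined protocol and SAP*

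**What the plan says.** Section A calls the trial double-blinded. Section G specifies who is masked: "The patient, research personnel and individuals collecting all objective outcome measures will be blinded to the randomization".

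Section H, under PRP Preparation, gives the procedure behind that statement. The paragraph that introduces the cup is restricted to one arm from its first words: "For each patient in the treatment arm of the study, the anesthesiologist will withdraw 10cc of venous blood". It then runs without a break. The blood is centrifuged and the PRP is mixed with calcium chloride and "placed within a sterile specimen cup that is covered in aluminum foil so that no one can see what is inside". Once the graft is harvested, "the autologous cancellous bone chips retrieved will be added to the specimen cup by the scrub technician". Of the chips and PRP together it says: "They will be left to soak within the concealed container until the end of the case". The section closes by claiming that three measures secure the blinding: hiding the cup's contents, preparing the PRP before study staff come in, and placing the chips after they have gone out.

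For controls there is much less. Section H confirms that "only those in the treatment arm will have blood withdrawn" and, under ACL reconstruction, mentions untreated cancellous chips as the alternative material applied to the harvest site. Section G defines the control arm as the reconstruction alone and does not mention chips. Neither section describes a container, a cover or a waiting period for control chips.

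On timing, section H says that once the graft is fixed and closure is about to begin, the senior surgeon and "any other research personnel present will leave the room".

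**The concern.** Foil hides what a cup holds. It does not hide that a cup is there, or that the scrub technician is putting bone into it. If only one arm has the cup, the concealment device itself becomes the cue.

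This matters because the outcome on which the trial is powered, kneeling pain on a visual analogue scale (section I), is a subjective patient report. It is collected at seven visits from 14 days to 24 months. Section F has patients complete the scales at postoperative office visits, and the surgeons go on examining them after surgery. A surgeon or staff member who knows the arm could colour what a patient expects or reports without entering any data. The objective side has a judgement element too: the IKDC examination form includes a harvest-site item graded from none to severe.

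**Working it through.** No arithmetic applies. The point does not depend on sample size, power or alpha, so the check is to follow the case in time and ask, at each stage, what differs between arms and who can see it.

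1. **Before the surgeon and research assistants enter.** Treatment arm: blood is drawn and PRP is prepared and put into the foil-covered cup. Control arm: no blood is drawn and nothing else is described. Section H keeps the surgeon and research assistants out until the blood has been drawn and the PRP is in the cup, so this stage is protected.

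2. **Graft harvest.** Treatment arm: the scrub technician adds the chips to the cup. Control arm: the handling of the chips is not described. The surgeon must be present, because section H has one of the two senior surgeons perform the reconstruction and leave only after graft fixation. Research staff may be present.

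3. **Rest of the operation up to fixation.** Treatment arm: the covered cup stays in the room with the chips soaking. Control arm: not described. The same people are in the room.

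4. **Just before closure.** The surgeon and any research personnel leave. The PRP Preparation text adds that anyone who will also be present for postoperative outcome measurement leaves at this point. That sentence is needed only if such people may have been in the room until then.

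5. **Placement of the chips.** A fellow or resident with no part in outcome collection does this. This stage is also protected.

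The protocol therefore closes off stages 1, 4 and 5. Stages 2 and 3 rely on the foil alone, and whether the foil is enough depends on something the text does not settle:

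- If every control has an identical cup handled in the same way, seeing a cup conveys nothing about the arm and the foil does its job.
- If controls have no cup, or a visibly different container, anyone who notices the cup and knows the procedure can infer the arm, and the exit before closure comes too late.

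On a literal reading only the treatment arm has a cup, because the whole sequence is governed by its opening restriction to that arm. No other section supplies a control counterpart.

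**The case against.** The strongest reply is that an omission is not a statement. Nowhere do the documents say that controls lack a cup, and there are signs that one was intended. Hiding the contents makes sense only if a cup might hold either material. Concealed contents are listed among the blinding measures. The closing paragraph of section H also refers to the cups in the plural. Most of this stands, although the plural is weak evidence, since that phrase is about adding PRP. It is why the point has to be stated conditionally.

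Several safeguards also narrow the exposure:

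- The patient is under general anaesthesia when blood is drawn and later marks the pain scales personally.
- The surgeons' own assessments are excluded from the data (sections F and G).
- Objective clinical data come from an independent researcher described as blinded, and imaging is read by a blinded radiologist (section F).
- Mixing is done in a separate preparation area, though still inside the operating room.
- The presence of research staff at surgery is written as a possibility, and no text places the section F assessors at harvest.

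All of these stand. They limit the route to bias but do not close it: the surgeon is always there at harvest, outcome staff may be, and both may meet patients later.

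A reader might infer that the cup gives away the arm in every case. That assumes both that controls have no cup and that everyone present notices and interprets it; the documents establish neither. A reader might also infer that the trial is not double-blind at all. That goes too far. Section G's list of those masked does not name the surgeon, and a surgeon's knowledge would not by itself unmask the patient or an assessor who was never in the room.

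**Conclusion.** The concern holds as a conditional gap in the written procedure. The cup, the loading of chips at harvest and the soak are specified for one arm only, during a period when people the protocol means to keep unaware are in the room. As written, the text does not support its own claim that these steps secure blinding. This is more than missing detail, because a team that followed the text literally would mask the surgeon and any staff present less well than the protocol promises.

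The conclusion rests on two assumptions: that controls are not in fact given a matching cup, and that the cup or its loading can be seen from where the surgeon and staff work. If either is false, the cue disappears and only the wording needs correcting.

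The remaining risk is that the surgeon, or research staff present at harvest, later influence the patient-reported pain scales or the objective examinations. The documents give no figure from which to derive either the share of cases affected or the resulting shift in pain score. It should be corrected, but it does not show that the outcome data would be biased.

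**What to change.** Add to section H, under PRP Preparation, that in every case an identical foil-covered specimen cup is set out before the surgeon and research staff enter, without PRP for controls; that harvested chips go into it in both arms; and that it is kept and handled in the same way until those people leave. State also that the equipment used to prepare PRP is either out of sight or present in every case, since a matching cup does not help if the centrifuge or double syringe is visible only in PRP cases.

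Reconcile section G's control-arm definition with the untreated chips mentioned in section H, and align the closing claim about blinding with the procedure as revised. Keeping outcome assessors out of the operating room for the whole case would protect the objective examinations as well, but it would not mask the surgeon, so it supplements the matching cup and does not replace it.

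The cost is a few sentences, plus one cup and foil per control case: about 50 × 1 = 50 sets for the 50 planned controls. The matching cup needs no control blood draw and no extra staff.
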